### **Secondary Immunologic Endpoints:**

1. Antigen-specific cellular immune responses to INO-3112 in blood samples obtained from study subjects per study schedule:
  - a) Interferon- $\gamma$  secreting T lymphocytes in PBMC by ELISpot
  - b) Flow Cytometry for T-cell activation, cytolytic phenotype, and memory phenotype in PBMC
2. Antigen-specific humoral responses to HPV-E6 and -E7 by ELISA per study schedule

### **Exploratory Clinical Endpoints:**

1. Changes in standard uptake volume (SUV) on PET/CT scans performed at baseline vs follow-up PET/CT scans obtained at specified time points.
2. Evaluation of subjects relative immune competence longitudinally throughout the study starting at the screening visit (for details refer to Section 6.7: Cervical Virologic and Peripheral Blood Immunogenicity Assessment)
3. Changes in cervical histology from the screening biopsy as compared to the week 16 biopsy
4. Local immune responses to INO-3112 in tumor tissue samples obtained at week 16
5. Disease-free survival assessed in accordance with RECIST v1.1 (Refer to Appendix 10) as follows:
  - Clinical evaluations for disease response will be conducted at all study visits, (as assessed by clinical signs and symptoms of disease progression).

- A baseline PET/CT scan will be obtained on each subject 1 to 2 weeks prior to Day 0 and then PET/CT scans for disease progression will be obtained for all subjects 3-4 months after Day 0 and every 3-5 months thereafter per standard of care/in accordance with local guidelines and institutional practices. Additional PET/CT scans may be obtained at other time points if clinically indicated to confirm a clinical diagnosis of disease progression based on signs and symptoms.

## 4 SELECTION AND ENROLLMENT OF SUBJECTS

### 4.1 Inclusion Criteria

- a) Written informed consent in accordance with institutional guidelines. If required by local law, candidates must also authorize the release and use of protected health information (PHI);
- b) Female subjects age 18 years or older;
- c) Histological diagnosis of squamous cell carcinoma, adenocarcinoma or adenosquamous cell carcinoma of the cervix. Not accepted are small cell, clear cell and other rare variants of the classical adenocarcinoma;
- d) Histologically confirmed, Stage IB-IVB, invasive cervical carcinoma associated with HPV-16 and/or HPV-18 and meeting the following eligibility criteria for either Cohort 1 or Cohort 2;
  1. Cohort 1
    - Newly diagnosed inoperable cervical cancer treated with chemoradiation therapy with curative intent and life expectancy of at least 12 months as assessed by the investigator
      - No CNS/spinal metastases
    - Able to initiate study treatment (Day 0) within 2 weeks of completion of last chemoradiation treatment;
      - Platinum based treatment (alone or in combination with other drugs); 5 weekly courses of Cisplatin 40 mg/m^2 completed within 10 weeks of its initiation
      - Standard radiation therapy (external beam and brachytherapy); completed within 10 weeks of its initiation
      - Brachytherapy; must be the last treatment if the subject is receiving sequential brachytherapy following the chemoradiation therapy
  2. Cohort 2
    - Persistent and/or recurrent cervical cancer
      - No CNS/spinal metastases
    - Able to initiate study treatment (Day 0) at least 2 weeks but no more than 4 weeks after completion of salvage therapy (If in the investigators opinion, there are no additional salvage therapy options, the subject may be enrolled in Cohort 2 without having received salvage therapy immediately prior to enrollment.)
    - Subject has a life expectancy of at least 12 months as assessed by the investigator

- e) ECG with no clinically significant findings as assessed by the investigator performed within 30 days of signing the informed consent form (ICF);
- f) Chemistry, liver function tests, renal function, total CPK and hematology lab results must be  $\leq$  Grade 1 at the time of screening, in accordance with the CTCAE v4.03;
- g) Eastern Cooperative Oncology Group (ECOG) Performance status of  $\leq$  1; ;
- h) Adequate venous access for repeated blood sampling according to study schedule;
- i) Women of child-bearing potential must have a negative serum pregnancy test and agree to remain sexually abstinent, have a partner who is sterile (i.e., vasectomy), or use two medically effective methods of contraception (e.g., oral contraception, barrier methods, spermicide, intrauterine device (IUD)). This requirement should be followed from screening through 24 weeks after last study treatment/EP. Whole pelvis external beam radiation therapy (EBRT) followed by intracavitary (IC) therapy for cervical cancer is considered to be an irreversible form of contraception;
- j) Able and willing to comply with all study procedures.

#### 4.2 Exclusion Criteria

- a) Pregnancy or breastfeeding;
- b) History of previous therapeutic HPV vaccination (individuals who have been immunized with licensed prophylactic HPV vaccines (e.g. Gardasil®, Cervarix®) are not excluded);
- c) Prior exposure to an investigational agent or device within 30 days of signing the ICF. Of note, the subject may participate in observational studies;
- d) Positive serological test for human immunodeficiency virus (HIV), Hepatitis B or Hepatitis C or history of HIV infection, Hepatitis B or Hepatitis C (women with cured HCV will be allowed; subject must have had an serologic test performed within 12 months of informed consent);
- e) Prior major surgery within 4 weeks of first study treatment/EP from which the subject has not yet recovered to baseline;
- f) High medical risks because of non-malignant systemic disease or with active uncontrolled infection;
- g) Current malignancies at other sites, with the exception of adequately treated basal or squamous cell carcinoma of the skin;
  - Cancer survivors, who have undergone curative therapy for a prior malignancy, have no evidence of that disease for five years and are deemed at low risk for recurrence, are eligible for the study;
- h) Congestive heart failure or prior history of New York Heart Association (NYHA) class III/ IV cardiac disease (refer to Appendix 8);
- i) Any concurrent condition requiring the continued use of systemic or topical steroids at or near the injection site, excluding non-systemic (e.g. inhaled and eye drop-containing) corticosteroids or the use of other immunosuppressive agents. All other corticosteroids must be discontinued  $>$  4 weeks prior to Day 0 of study product administration;
- j) Any cardiac pre-excitation syndromes (such as Wolff-Parkinson-White);

- k) History of seizures (unless seizure free for 5 years);
- l) Less than two acceptable sites exist for IM injection and EP between use of the deltoid and lateral quadriceps muscles. A site for injection/EP is not acceptable if there are tattoos or scars within 2 cm of the injection/EP site or if there is implanted metal within the same limb. Any device implanted in the chest (e.g., cardiac pacemaker or defibrillator) excludes the use of the deltoid muscle on the same side of the body;
- m) Administration of any non-study related vaccine within 2 weeks of Day 0;
- n) Active drug or alcohol use or dependence that, in the opinion of the investigator, would interfere with adherence to study requirements;
- o) Imprisonment or compulsory detainment (involuntary incarceration) for treatment of either a psychiatric or physical (i.e. infectious disease) illness;
- p) History of immunosuppressive or autoimmune disease;
- q) Any other illnesses or conditions that in the opinion of the investigator may affect the safety of the subject or limit the evaluation of a subject or any study endpoint.

#### **4.3 Supplementation of Study Subjects**

Additional subjects may be enrolled with the approval of medical monitor, if subjects withdraw prior to completion of the study treatment.

#### **4.4 Discontinuation/Withdrawal of Study Subjects**

The subject will be considered to have completed the study when she completes all scheduled Study Treatments and follow-up visits or death, whichever occurs first. The discharge visit will be the last follow-up visit. If subject discontinues or is withdrawn at any time after receipt of Study Treatment, the investigator should make every effort to have the subject complete all assessments designated for the discharge visit. The investigator will make every effort to have all scheduled immune assessment blood sample collected as indicated in the Schedule of Events, Table 1 of the Clinical Synopsis. Any adverse events (AEs) present at the time of discontinuation/withdrawal should be followed in accordance with the safety requirements outlined in Section 7.1 – Safety Parameters.

If the subject manifests Grade 4 toxicity attributable to study treatment/EP, she will not receive further study treatment/EP but will be encouraged to continue follow-up safety assessment through study discharge and not discontinue from the study. If a subject manifests Grade 3 toxicity attributable to study treatment/EP, the medical monitor and PI will discuss whether further treatment should be continued for that participant.

Subjects will be discontinued from the study if there is confirmed disease progression or if subject starts new anti-cancer therapy.

The reason for any discontinuation of study treatment should be discussed with the Sponsor's Medical Monitor within 24 hours. The primary reason for the subject discontinuing further study treatments or withdrawal from the study itself should be selected from the following standard categories:

- Adverse Event (Adverse Reaction): Clinical or laboratory events occurred that, in the medical judgment of the investigator for the best interest of the subject, are grounds for discontinuation. This includes serious and non-serious adverse events regardless of relation to study treatment.
- Death: The subject died.
- Withdrawal of Consent: The subject desired to withdraw from further participation in the study in the absence of an investigator-determined medical need to withdraw. If the subject gave a reason for withdrawal, it should be recorded on the Case Report Form (CRF). This reason does not allow for further data collection and should not be selected if follow-up data collection of this subject is anticipated by the subject.
- Protocol Violation: The subject's findings or conduct failed to meet the protocol entry criteria or failed to adhere to the protocol requirements (e.g., treatment noncompliance, failure to return for defined number of visits). The violation should be discussed with the Sponsor's Medical Monitor prior to discontinuation of Study Treatments or study withdrawal.
- Lost to Follow-up: The subject fails to attend study visits and study personnel are unable to contact the subject after repeated attempts including letter sent by certified mail or equivalent.
- Physician Decision: The subject was terminated for a reason other than those listed above by the physician caring for the subject.
- Other: The subject was terminated for a reason other than those listed above, such as termination of study by the Sponsor.

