### **Primary Safety Endpoints:**

1. Incidence of adverse events (all, severe [graded per CTCAE v4.03], unexpected, serious) classified by system organ class (SOC), preferred term, severity, and relationship to study medication and schedule
2. Injection site reactions including pain, tenderness, erythema and induration at administration site
3. Rates of acute gastrointestinal, genitourinary, or other chemoradiation side effects above the expected, graded per Acute Radiation Morbidity Scoring Criteria (RTOG)
4. Changes in laboratory parameters from baseline

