The following study evaluations will be performed on **Weeks 24 (±2 weeks):**

- Medical/clinical assessment
- Targeted physical assessment (including ECOG performance status)
- AE/SAE assessment
- Concomitant medications
- Vital Signs and Weight
- Whole blood and serum for immunologic assays

The following study evaluations will be performed on **Weeks 32 (±2 weeks):**

- Medical/clinical assessment with ROS
- Targeted physical assessment (including ECOG performance status)
- AE/SAE assessment
- Concomitant medications

- 
- Vital Signs and Weight
  - PET/CT scan
  - Whole blood and serum for immunologic assays

The following study evaluations will be performed on **Week 36 or discharge visit (±2 weeks):**

- Medical/clinical assessment
- Full physical exam (including ECOG performance status)
- AE/SAE assessment
- Concomitant medications
- Determine disease status
- Vital Signs and Weight
- PET/CT scan (not required if performed at wk 32)
- ThinPrep™ sample for HPV testing (if applicable)
- Digene swab (2 samples) (if applicable)
- Whole blood and serum for immunologic assays

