#### **6.5 Assessment of Laboratory Abnormalities**

Investigators may use clinical judgment to enroll subjects with isolated Grade 1 abnormalities in screening CBC, serum chemistry or CPK values if there is no indication of disease process in the remainder of the history and physical examination.

Blood will be drawn for serum chemistry, hematology and serology assessments as well as pregnancy testing at screening for inclusion into the study as listed in sections 6.2.4.8 and 6.2.4.9.

Urinalysis will be performed at screening to fulfill eligibility criteria. CPK will be performed at Screening and Week 16.

Complete blood count with differential and serum chemistry will be performed at each study treatment/EP and Week 16.

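### The early discharge visit has no CBC, serum chemistry or CPK, so a subject who leaves before her next scheduled draw has no post-dose laboratory result for her last dose

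*Combined protocol and SAP*

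**What the plan says.** Section 4.4 sets three tasks for a subject who stops after receiving study treatment.

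- Discharge visit: "the investigator should make every effort to have the subject complete all assessments designated for the discharge visit".
- Immunology blood: "The investigator will make every effort to have all scheduled immune assessment blood sample collected as indicated in the Schedule of Events".
- Adverse events: "Any adverse events (AEs) present at the time of discontinuation/withdrawal should be followed in accordance with the safety requirements".

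A subject taken off treatment for attributable Grade 4 toxicity is treated differently. She "will be encouraged to continue follow-up safety assessment through study discharge and not discontinue from the study".

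The discharge assessments are those listed in Section 6.1.2 under "Week 36 or discharge visit (±2 weeks"). They are clinical assessment, full examination with ECOG status, AE/SAE review, concomitant medications, disease status, vital signs and weight, PET/CT, ThinPrep, Digene swabs and immunology blood. Table 1 agrees: its Week 36 column is empty for CBC, chemistry, CPK and post-treatment reaction.

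On laboratory timing, Section 6.5 says "Complete blood count with differential and serum chemistry will be performed at each study treatment/EP and Week 16" and "CPK will be performed at Screening and Week 16". Table 1 (footnote o) and Section 6.2.4.9 require treatment-visit samples to be taken within the 48 hours before the dose.

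The fourth primary safety endpoint in Section 3 is "Changes in laboratory parameters from baseline". Section 8.6 rules out imputation.

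**The concern.** The discharge list suits a subject at Week 36, which is 24 weeks after the last dose (36 − 12), when safety laboratory tests have already been completed at Week 16. Section 4.4 applies the same list to a subject who may have been dosed days earlier. Because each treatment-visit sample precedes its dose, it can only show the effect of earlier doses. The sample that would show the effect of the last dose is the one at the next visit, which an early leaver never reaches.

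This bears on a primary safety endpoint. The losses are unlikely to be random: Section 4.4 lists adverse events, including laboratory events, as a reason for leaving, and it requires discontinuation on confirmed progression or new anti-cancer therapy. The first follow-up scan is due 3 to 4 months after Day 0, which is about Week 13 (3 × 52/12) to Week 17 (4 × 52/12). Progression found before the Week 16 panel is therefore foreseeable, particularly in Cohort 2. Without imputation, the post-dose laboratory summary for the last dose would describe mainly the subjects who stayed. The Grade 3 and 4 counts in the stopping rules (Section 7.5.3) also cannot include an asymptomatic laboratory event that was never sampled.

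**Working it through.** **Inputs.** Doses are at Weeks 0, 4, 8 and 12 (Section 3). CBC and chemistry are drawn at screening, before the dose at Weeks 0, 4, 8 and 12, and at Week 16; CPK is drawn at screening and Week 16 (Section 6.5, Table 1). Neither document section nor Table 1 schedules any of these at Weeks 24, 32 or 36. No dropout rate is given.

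**Coverage.** A dose counts as covered if a scheduled draw follows it before the subject leaves.

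| Leaves | Doses given | Doses followed by CBC/chemistry | Last dose covered | Post-dose CPK |
|---|---|---|---|---|
| After dose 1, before Week 4 samples | 1 | 0 | No | None |
| After dose 2, before Week 8 samples | 2 | 1 | No | None |
| After dose 3, before Week 12 samples | 3 | 2 | No | None |
| After dose 4, before Week 16 panel | 4 | 3 | No | None |
| After Week 16 panel | 4 | 4 | Yes | Yes |

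One case falls outside the table. If the Week 4, 8 or 12 samples are drawn and the dose is then withheld, the last dose given is covered for CBC and chemistry. CPK is still missing if she leaves before Week 16.

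**The plan's own figures (Section 8.1).** With n = 10 and a 23% rate of Grade 3 or 4 hematologic toxicity, the chance of at least one event is 1 − 0.77^10 = 92.7%, against a stated value of approximately 92%. The two-sided 95% Clopper-Pearson upper limit for 0 of 10 is 1 − 0.025^(1/10) = 30.8%, against a stated <31%. Both are reproduced.

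**Illustration.** Assume that 1, 2 or 3 of the 10 subjects contribute no post-dose result and are not replaced. The formulas become 1 − 0.77^n and 1 − 0.025^(1/n).

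| Subjects with a post-dose result | Chance of ≥1 event at 23% | Upper limit for 0 of n |
|---|---|---|
| 10 | 92.7% | 30.8% |
| 9 | 90.5% | 33.6% |
| 8 | 87.6% | 36.9% |
| 7 | 84.0% | 41.0% |

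For CBC these rows apply only to subjects who leave after dose 1 and before the Week 4 samples, because later leavers still contribute some post-dose results. For CPK the upper-limit column applies to every leaver before Week 16. Section 8.1 makes no statement about CPK, so that use is by analogy. The 23% rate does not apply to CPK.

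**The case against.** The strongest reply is that the gap is narrow and other provisions limit it.

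- **Not every early leaver is affected.** A reader might infer that anyone leaving before Week 36 lacks post-dose laboratory data. Leavers in the last 20 of the 36 weeks have the full Week 16 panel, and a subject whose dose is withheld after her samples are drawn has CBC and chemistry. This stands and limits the point.
- **Injection sites.** The discharge list has no injection-site line, so a reader might infer that no check is made. Sections 6.4 and 7.3 already call for one at the next visit. The texts need reconciling, but the check is not absent from the plan.
- **Subjects off treatment for Grade 4 toxicity.** Section 6.5 ties CBC and chemistry to each treatment, which might suggest that these subjects lose their samples. Section 6.2.4.9 refers other visits to Table 1, which lists the tests by week. Only the wording needs aligning.
- **Safety net.** Adverse events present at withdrawal are followed, and a clinically significant laboratory change is recorded as an adverse event (Section 7.2.1). This protects against known abnormalities. It does not produce a sample that would reveal an unrecognised one.
- **Replacement.** Section 4.3 permits additional subjects when someone withdraws before completing treatment. That is discretionary; it can restore the count but not the leaver's own results.
- **CPK is sparse for everyone.** Completers also have a single post-dose CPK, and Section 1.3.1 reports unremarkable CPK after electroporation in an earlier study. This is true, but a leaver before Week 16 loses even that one value.

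Unscheduled tests remain possible at the investigator's discretion, but nothing in the plan requires or standardises them.

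**Conclusion.** The point holds within these limits. A subject who leaves between a dose and her next scheduled draw has no protocol-required CBC or chemistry after that dose. One who leaves after dose 1 and before the Week 4 samples has none after any dose. Every subject who leaves before the Week 16 panel has no post-dose CPK. The coverage result rests only on the schedule as written.

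The effect on precision depends on an assumed number of leavers. With 1 to 3 of 10 lost and not replaced, a zero-event upper limit moves from 30.8% to between 33.6% and 41.0%. It would be wrong to conclude from this that the <31% in Section 8.1 is an error: it is stated for 0 of 10, follows a calculation on hematologic toxicity, and is reproduced. The more important consequence is that the missing results come from subjects whose departure may be related to toxicity or progression. This is a gap worth closing because closing it is cheap; it does not invalidate the design.

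**What to change.** - In Sections 4.4 and 6.1.2 and a Table 1 footnote, state that a discharge visit held early includes CBC with differential and serum chemistry if none has been drawn since the last dose, and CPK if the Week 16 CPK has not been done. This trigger avoids repeating CBC and chemistry in a subject whose samples were drawn before a dose was withheld.
- Reconcile the discharge list with Sections 6.4 and 7.3, so that the injection-site assessment they call for appears there when the discharge visit is the next visit after a dose.
- Align the Section 6.5 wording with the Table 1 weeks for subjects who are off treatment but still in follow-up.

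The cost is a short amendment and about one extra tube at a visit where immunology blood is already taken. The change alters no dose and no treatment rule. It cannot recover data from subjects who withdraw consent to further data collection or who are lost to follow-up.

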## 5 INVESTIGATIONAL PRODUCTS

### 5.1 Investigational Product

Investigational product is defined as a pharmaceutical form of an active ingredient being tested or used as a reference in the study, whether blinded or unblinded.

INO-3112 is combination of VGX-3100 and INO-9012.

VGX-3100, the active investigational product to be used in this study, is a mixture of two separate DNA plasmids encoding E6 and E7 proteins of HPV types 16 and 18. A second investigational product being evaluated for use in combination with VGX-3100 is known as INO-9012. INO-9012 is a DNA plasmid expressing the p35 and p40 human IL-12 subunits off of separate promoters within the same plasmid.

INO-3112 will be provided by Inovio or its designee. The site pharmacist or designee will combine VGX-3100 and INO-9012 into a single syringe to create a 1.1 mL IM formulation of INO-3112 (see Appendix 6 for details).

**Table 5.1 Investigational Products**

VGX-3100	The plasmid pGX3001 and pGX3002
Volume per container	1.0 mL minimum/vial

Concentration	6.0 ± 0.4 mg/mL
Container Size and Type	10 mL glass vial
INO-9012	The plasmid pGX6001
Volume per container	0.2 mL minimum/vial
Target Concentration	10.0 ± 0.5 mg/ml
Container Size and Type	2 mL glass vial

## 5.2 Packaging and Labeling

This study is open label. Therefore the subject, the Investigator’s site personnel and the Sponsor are not blinded to treatment. Each vial will be labeled with a single panel label. The following shows text that may be included on the vial labels:

Biologic Product	Specimen Label
VGX-3100	SynCon™ VGX-3100 [6mg/mL] 1 mL/vial Lot: VGX-3100. xxxxxx Date of Manufacture: DD MMM YY Final Retest Date: DD MMM YY Store frozen at or below -15C CAUTION: New Drug – Limited by Federal Law to Clinical Trial Use Only Inovio Pharmaceuticals Inc [name] USA
INO-9012	SynCon™ INO-9012 [10 mg/mL] 0.2 mL/vial Single Use Vial Lot: INO-9012.xxxxxx Date of Manufacture: DD MMM YY Final Retest Date: DD MMM YY Store frozen at or below -15°C CAUTION: New Drug – Limited by Federal Law to Investigational Use. Inovio Pharmaceuticals Inc. Rev 000

